"Tolerance to Baked Foods in Children Under 6 Years Old Allergic to Cow's Milk and Egg Proteins"

PIC-104-14

6 November 2014

TOLERANCE TO BAKED FOODS IN CHILDREN UNDER 6 YEARS OLD ALLERGIC TO COW'S MILK AND EGG PROTEINS

1) CURRENT STATUS OF THE TOPIC

Food allergy is a condition with increasing prevalence in Western countries. It is estimated that 5–8% of children in our environment are allergic to at least one food, compared to 1–2% in adults. This condition significantly impacts quality of life and social activities, causing emotional and familial stress. The most common IgE-mediated food allergens are cow's milk, egg, nuts, fish, and shellfish. To date, the accepted treatment is the strict avoidance of the allergen, which carries the ongoing risk of accidental exposure and potential nutritional deficiencies.

Oral immunotherapy (OIT) for specific food allergens has emerged as a treatment option for patients who do not outgrow their allergy in early childhood. Current studies suggest a higher likelihood of developing tolerance in patients undergoing OIT compared to those following only an elimination diet; however, local and systemic adverse effects, sometimes severe, can occur during treatment. Therefore, including a patient in OIT requires a careful risk-benefit analysis of possible severe reactions during treatment versus the long-term benefit of immune tolerance.

Recently, studies have focused on the potential for tolerance to baked foods. Heating food changes the protein's structure, reducing allergenicity by destroying conformational IgE-binding epitopes. This appears to be key in acquiring tolerance to milk and egg proteins. Additionally, baking within a cereal matrix further reduces allergenicity by altering digestibility or making epitopes less accessible. This effect varies depending on the food; for example, heating peanut proteins may actually increase allergenicity due to glycosylation.

The immunological changes observed in a diet including baked milk or egg are similar to those seen with OIT, but the baked food approach is generally safer and provides a more natural immunomodulatory strategy. OIT can be challenging due to the risk of serious adverse effects. Introducing baked foods into the diet not only improves quality of life by increasing dietary variety but also reduces stress in social settings. According to recent studies, this strategy may help shorten the time needed to achieve full tolerance.

Since 2006, the Hospital Sant Joan de Déu in Esplugues has successfully implemented OIT protocols for milk and egg in children over 5 years of age, accepting the associated risks. However, complete permanent desensitization has not been achieved in all patients. Many still experience occasional adverse reactions during maintenance. The success rate is estimated at around 70%, with failure mainly affecting children with anaphylaxis—those who would most benefit from protection.

2) OBJECTIVES

Main objective: To evaluate tolerance to baked foods in children under 6 years old who are allergic to cow's milk or egg proteins.

Secondary objectives:

- To evaluate tolerance to raw foods after one year of controlled intake of baked foods containing milk or egg in increasing amounts.
- To assess the immune response by identifying biomarkers that may predict the acquisition of tolerance.

- To compare quality-of-life questionnaires between patients tolerant to baked foods and their families versus those in the control group.
- To determine the individual reaction threshold dose that would allow patients to consume trace amounts of the allergen, thereby improving their quality of life and nutritional status.

3) METHODOLOGY

This is a prospective interventional study.

Inclusion criteria for cow's milk (CM):

- Children aged 12 months to 6 years with a clinical history suggestive of cow's milk protein allergy, and positive specific IgE and/or skin prick tests.

Inclusion criteria for egg:

- Children aged 12 months to 6 years with a clinical history suggestive of egg allergy, and positive specific IgE and/or skin prick tests.
- Children aged 12 months to 6 years sensitized to egg proteins (positive specific IgE and/or skin prick tests) without prior ingestion.

Exclusion criteria:

- Patients whose guardians do not sign the informed consent form (Annex 1).
- Patients with heart disease or conditions contraindicating the use of epinephrine.
- Patients who are already consuming baked products with milk or egg.

Complementary evaluations:

Skin prick tests, specific IgE, IgA, and IgG4 levels, regulatory T cells, IL-4, IL-5, IL-10, and TGF- β will be assessed at the beginning of treatment (T0) and after 12 months (T1). Basophil activation tests with cow's milk or egg proteins will also be performed before and after treatment.

Eligible patients will undergo a baked food oral food challenge (OFC) at baseline. After 12 months of controlled intake, they will undergo another OFC with cooked and raw forms of the allergen.

Validated quality-of-life questionnaires for food allergy will be administered to families and children (depending on age) at baseline, during hospitalization for OFC, and at 12 months.

All OFCs will be performed at the hospital in a setting equipped to manage potential adverse reactions. Skin and blood tests will be performed 15 to 30 days before starting treatment.

BAKED FOOD CHALLENGE PROTOCOLS

Initial baked milk challenge:

Conducted using commercially available 6-cereal cookies (Almirón®), each containing 0.275 g of milk protein.

- Dose 1: 0.0375 g protein (1/8 cookie)
- Dose 2: 0.075 g protein (1/4 cookie)
- Dose 3: 0.15 g protein (1/2 cookie)
- Dose 4: 0.275 g protein (1 full cookie)
- Dose 5: 0.55 g protein (2 cookies)

Doses administered at 30-minute intervals. Vital signs are monitored before and after each dose. Observation continues for 3 hours post-final dose.

Initial baked egg challenge:

Conducted using Damira® cookies (free of cow's milk):

- Dose 1: ½ cookie (0.11 g protein)
- Dose 2: 1 cookie (0.22 g protein)
- Dose 3: 2 cookies (0.44 g protein)
- Dose 4: 5 cookies (1.1 g protein)

Doses administered at 30-minute intervals for the first two, then 60-minute intervals. Vital signs are monitored before and after. Observation continues for 3 hours post-final dose.

Cow's milk challenge:

Using pasteurized milk (3g/100mL) per PRACTALL protocol, followed by 125–200 mL final dose:

CM-OFC (ml)	CM-OFC (g)	Interval (minutes)
0.1	0.003	30
0.3	0.01	30
1	0.03	30
3	0.1	30
9	0.3	30
30	1	30
90	3	120
125/200	3.75/6	180 observation

Cooked egg challenge:

6-step protocol: 0.3, 1, 3, 9.5, and 30 g of hard-boiled egg white + 1 well-cooked omelet (7.5 g protein). Administered at 30-minute intervals (first 5 doses) and 120 minutes for final dose.

6-month dose escalation:

- Baked milk: 4 Almirón® cookies = 1.1 g milk protein.
- Baked egg: 1 homemade muffin (recipe in Annex 1) = 2 g egg protein. 3-hour observation post-dose.

4) STATISTICAL ANALYSIS

All data will be analyzed using SPSS Version 26 (IBM Corp., USA) and/or GraphPad Prism Version 9 (GraphPad Software, Inc., La Jolla, Calif). Descriptive statistics will be performed for the total sample, as well as for the control and intervention groups. Results with p-values < 0.05 will be considered statistically significant.

Participants will be categorized as tolerant or non-tolerant based on their ability to tolerate 1 g of cow's milk protein or 2 g of egg protein. Student's t-test will be used to compare means of predictive variables. Differences in the distribution of clinical variables will be assessed using the Chi-square test or Fisher's exact test for categorical variables. For non-parametric data, the Mann-Whitney U test or Kruskal-Wallis test will be applied.

Receiver Operating Characteristic (ROC) curve analysis will be conducted to evaluate the diagnostic performance of each individual biomarker in predicting tolerance to baked

products. The accuracy of the test will be assessed using the area under the ROC curve (AUC), with an AUC > 0.7 considered acceptable. The performance of optimal cut-off points will be described in terms of sensitivity and specificity.

5) WORK PLAN AND TIMELINE

The principal investigator will be [name] [name]. Each study group will be led by a physician: Dr. [name] for egg-allergic patients and Dr. [name] for cow's milk protein-allergic patients. Data collection and processing will be handled by Dr. [name] and Dr. [name]. Laboratory determinations will be carried out by Dr. [name] (Hospital Clínic) and Dr. [name] (Hospital Sant Joan de Déu). All physicians and nurses in the department will be direct collaborators.

Patient recruitment will last 2 years. Approximately 80 patients will be included: 30 allergic to egg, 30 allergic to cow's milk protein, and 20 controls. Each patient will be followed for 12 months after randomization.

6) BUDGET

The principal investigator, responsible physicians, and collaborators will conduct the project within regular working hours without additional personnel costs. The main expenses are for laboratory studies, detailed below:

Study	Price per sample (€)
PBMC isolation	15
Antigen-specific proliferation assay	30
TH1/TH2/FOXP3 cytometry panel	60
BAT	99
Specific IgA determination	12
IgG4 determination	19

Estimated costs for 60 patients (T0)	Price 60 patients (euros)
PBMC isolation	900
Antigen-specific proliferation	1800
BAT	5940
Specific IgA	720
TOTAL	9360

This does not include cytokine determination via Luminex, cytometry panel TH1/TH2/FoxP3 (€3600), and IgG4 determination (€1140), which will require other grants. T1 determinations are also pending funding.

Luminex cytokine analysis is the most expensive: one plate (~€2200-2500) analyzes 8 patients. For 60 patients, the cost is approximately €20,000, which exceeds this grant's budget. Therefore, supernatants will be frozen and analyzed once funding is available.

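### The quality-of-life objective compares baked-tolerant children with controls who have no stated tolerance rule, so selection alone could produce a difference

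*Combined protocol and SAP*

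**What the plan says.** All references are to the combined protocol and SAP.

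- Section 2 (Objectives) lists as a secondary aim: "To compare quality-of-life questionnaires between patients tolerant to baked foods and their families versus those in the control group".
- Section 5 (Work plan and timeline) gives the sizes: "Approximately 80 patients will be included: 30 allergic to egg, 30 allergic to cow's milk protein, and 20 controls". It also contains the only mention of randomization: "Each patient will be followed for 12 months after randomization". No method, ratio or point of randomization is given, and the controls are not described further.
- Section 3 (Methodology) states: "Eligible patients will undergo a baked food oral food challenge (OFC) at baseline". After 12 months of controlled intake there is a further challenge with cooked and raw food. Questionnaires are taken at baseline, around the challenge admission, and at 12 months.
- Section 4 (Statistical analysis) states: "Descriptive statistics will be performed for the total sample, as well as for the control and intervention groups". It classes participants as tolerant or not by 1 g of milk protein or 2 g of egg protein, without naming the challenge or time point. It lists t, chi-square, Fisher, Mann-Whitney and Kruskal-Wallis tests and a general 0.05 threshold. None of these tests is assigned to quality of life, and none adjusts for baseline.
- Section 6 (Budget) costs the T0 laboratory work for 60 patients.

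**The concern.** A fair comparison needs the same entry rule on both sides. Here one side is restricted by a challenge result and the other, as written, is not. If the controls include children who would not tolerate baked food, the two sides differ in case mix before anyone eats anything.

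That matters only if tolerance is related to quality of life, for example through severity. The documents support one half of this path, and only by analogy. Of the hospital's oral immunotherapy, section 1 says: "The success rate is estimated at around 70%, with failure mainly affecting children with anaphylaxis". The other half, that severity affects quality of life, is an assumption.

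The background section also says: "Introducing baked foods into the diet not only improves quality of life by increasing dietary variety but also reduces stress in social settings". With that expectation already in print, a significant difference would be easy to read as an effect of the diet when part or all of it could be selection.

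**Working it through.** **Figures in the plan.** The group sizes add up: 30 + 30 + 20 = 80. No SD, effect size, tolerance rate or power is given, so there is no other figure to reproduce. The 0.05 level is taken as two-sided, which the plan does not state.

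**Assumed inputs (not in the documents).** 60 intervention children and 20 unselected controls; tolerant share q = 0.5 or 0.7; correlation r = 0.2 to 0.5 between the liability to be tolerant and quality of life; no intervention effect; scores in SD units. The only success rate given, about 70%, is for oral immunotherapy in children over 5, not for baked food.

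**1. False shift.** If children on the tolerant side of a normal cut make up share q, their mean exceeds that of unselected children by r × φ(z)/q, where z is the normal quantile of q.
- q = 0.7: φ(z)/q = 0.497, so the shift is 0.099 (r = 0.2) to 0.248 (r = 0.5).
- q = 0.5: φ(z)/q = 0.798, so the shift is 0.160 to 0.399.

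**2. Rejection rate, unadjusted.** SE = √(1/n₁ + 1/20). Rejection = Φ(shift/SE − 1.96) + Φ(−shift/SE − 1.96).

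| Tolerant share | n₁ v 20 | SE | Shift (SD) | Rejection |
|---|---|---|---|---|
| 0.7 | 42 | 0.272 | 0.10-0.25 | 6.5-15.0% |
| 0.5 | 30 | 0.289 | 0.16-0.40 | 8.6-28.2% |

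A second route gives similar results. If tolerant and non-tolerant children differ by d, the shift is (1 − q)d. For d = 0.3 to 0.8 this is 0.09-0.24 SD at q = 0.7 and 0.15-0.40 SD at q = 0.5. At q = 0.9 it falls to 0.03-0.08 SD, with simulated rejection of 5.1-6.3%.

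**3. Weaker link.** Step 1 takes r as the correlation with tolerance liability itself. If the path runs through severity, and severity correlates with that liability at only 0.5 (assumed), the shift halves:
- q = 0.7: 0.05-0.12 SD and 5.4-7.4% rejection.
- q = 0.5: 0.08-0.20 SD and 5.9-10.6% rejection.

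**4. ANCOVA on baseline, controls still unselected.** Simulation of 5,000 trials per setting, baseline/12-month correlation ρ = 0.5 or 0.7, liability equal to severity as in step 1:
- r = 0.2: remaining shift 0.03-0.08 SD, rejection 5.1-6.4%.
- r = 0.5: remaining shift 0.08-0.23 SD, rejection 7.4-14.5%.
- r = 0: rejection 4.7-5.4%.

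**5. Same rule on both sides, genuinely randomized controls, ANCOVA.** All 60 v 20: 4.4-5.7%. Tolerant v tolerant controls: 4.8-5.6%. Both are at nominal level within simulation error.

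**6. Which time point defines tolerance?** Section 3 baseline egg doses: 0.11 + 0.22 + 0.44 + 1.1 = 1.87 g, below the 2 g criterion in section 4. The 6-month egg step is 2 g. Baseline milk doses: 0.0375 + 0.075 + 0.15 + 0.275 + 0.55 = 1.0875 g, and the 6-month milk step is 1.1 g, so the 1 g milk criterion is reached at either point. The egg criterion therefore leaves open a 6-month definition. That would select children after randomization even if only those who passed the baseline challenge were randomized.

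**7. Power cost.** Detectable benefit at 80% power is 2.8 × √(1/n₁ + 1/n₂) × √(1 − ρ²), for ρ = 0.5 and 0.7, with only tolerant children benefiting.

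| Comparison | q = 0.7 | q = 0.5 |
|---|---|---|
| Tolerant v all 20 controls | 0.659, 0.543 | 0.700, 0.577 |
| Tolerant v tolerant controls (42 v 14; 30 v 10) | 0.748, 0.617 | 0.885, 0.730 |
| All 60 v 20 (0.626, 0.516, divided by q) | 0.894, 0.738 | 1.252, 1.033 |

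Against the first row, the as-allocated comparison needs a benefit 1.36 or 1.79 times as large. Tolerant v tolerant needs 1.14 or 1.26 times.

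**The case against.** The strongest reply is that the text may already describe a fair design. Section 3 challenges eligible patients and section 4 classes participants, and neither excludes controls. The 12 months of follow-up from randomization match the 12 months of controlled intake, which fits randomization at the start of intake, after the challenge. On that reading only tolerant children are allocated and the written contrast is sound. This is plausible and cannot be ruled out. But being challenged and classed is not being selected, and no sentence uses the result to decide who enters the control side.

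It is also fair to say that no quality-of-life test is specified, so the rejection rates describe a test supplied here, and that the objective says only that groups will be compared.

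A reader might draw four stronger conclusions that the documents do not support:
- That the comparison is biased as designed. The order of challenge and randomization is missing, so this is not shown.
- That the 60-patient budget proves controls are not challenged. It covers laboratory assays at T0 and says nothing about food challenges.
- That 28% is this trial's false-positive rate. It is the upper end of an illustration in which severity, if that is the path, determines tolerance completely.
- That there are only two possible designs. Controls might be children who failed the challenge, or children outside the two allergic groups. The illustration covers neither.

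**Conclusion.** The point stands in conditional form. The contrast has a stated tolerance filter on one side only, and the plan does not supply the facts that would show whether this matters. Two conditions are both needed for a spurious difference: controls not selected on the same tolerance result, and a relation between tolerance and quality of life. The bias vanishes if either fails. Randomizing only children who passed the baseline challenge is enough only if tolerance is also judged at that challenge, which the 2 g egg criterion leaves in doubt.

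The size rests wholly on assumed tolerance shares and correlations. It ranges from negligible (weak correlation with baseline adjustment, or most children tolerant) to material (half tolerant, correlation 0.5, unadjusted). Because this is a secondary objective and the bias is conditional, it should be corrected but does not threaten the main objective. Confidence is medium.

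**What to change.** 1. **Analysis.** Analyse the 12-month score by ANCOVA on the baseline score, with allergen as covariate, and record each control's allergen. This adds precision but does not by itself remove the selection.
2. **Population.** Say who the controls are and where randomization falls, then apply one rule to both sides.
   - If only baseline-tolerant children are randomized, keep the written contrast.
   - If randomization precedes the tolerance classification, make all intervention children v all controls, as allocated, the inferential comparison. Use tolerant v tolerant controls only if controls already take the same challenge.
   - If controls are not randomized, report the tolerant-only contrast descriptively, with no claim of a diet effect.
3. **Time point.** State which time point defines tolerance for this comparison. Reconcile the section 4 egg criterion with the section 3 baseline egg challenge total and the 6-month step.

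**Cost.** These are text changes. The baseline and 12-month questionnaires are already planned, and no new procedures are required. The price is power: where the as-allocated comparison applies, the benefit among tolerant children must be 36% larger (70% tolerant) to 79% larger (50% tolerant) to be detected than with the tolerant-only contrast. There is no penalty if only tolerant children are randomized.

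### The egg group admits sensitised children who have never eaten egg, yet the plan calls the group allergic and specifies no reporting by entry route

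*Combined protocol and SAP*

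**What the plan says.** Section 2 gives the main objective as "To evaluate tolerance to baked foods in children under 6 years old who are allergic to cow's milk or egg proteins". A secondary objective concerns "identifying biomarkers that may predict the acquisition of tolerance".

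Section 3 gives egg two entry routes for children aged 12 months to 6 years. The first requires a "clinical history suggestive of egg allergy, and positive specific IgE and/or skin prick tests". The second admits children "sensitized to egg proteins (positive specific IgE and/or skin prick tests) without prior ingestion". Cow's milk has one route only, a "clinical history suggestive of cow's milk protein allergy, and positive specific IgE and/or skin prick tests".

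On challenges, section 3 states: "Eligible patients will undergo a baked food oral food challenge (OFC) at baseline". It continues: "After 12 months of controlled intake, they will undergo another OFC with cooked and raw forms of the allergen". Section 1 explains that heating changes the protein, "reducing allergenicity by destroying conformational IgE-binding epitopes".

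Section 4 plans descriptive summaries for everyone together and for the control and intervention groups. It classes egg participants as tolerant or not by one threshold of 2 g of egg protein, and plans ROC curves for tolerance to baked products. Entry route is not mentioned. Section 5 counts 30 egg-allergic children, 30 milk-allergic children and 20 controls, without saying how the controls divide by food.

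**The concern.** The plan itself distinguishes a sensitised child from one with a suggestive history when it sets the egg criteria. The distinction then disappears from the objective, the sample size and the analysis. A positive specific IgE or skin prick test in a child who has never eaten egg shows sensitisation; it does not show clinical reactivity.

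The baseline challenge only partly restores the distinction. A sensitised-only child who reacts to baked egg has shown reactivity. One who passes could be allergic but tolerant of the baked form, or never allergic. The baseline skin, IgE and basophil tests are informative, but the plan gives no rule for using them to tell these two apart.

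At stake is the population to which the egg result belongs. A tolerance rate stated for egg-allergic children could include children with nothing to outgrow, and such children could also be counted as tolerant at 12 months.

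**Working it through.** **1. The plan's own figure.** 30 egg + 30 milk + 20 controls = 80, as section 5 states. The documents give no tolerance rate, power or dropout, so there is no sample-size calculation to reproduce.

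**2. Where the routes could be separated.**

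| Step | Separates sensitised-only from history-positive children? |
|---|---|
| Egg inclusion criteria (section 3) | Yes, by the criterion met |
| Main objective (section 2) and sample size (section 5) | No, all called allergic |
| Baseline challenge (section 3) | Baked food only; a pass does not settle whether the child was ever allergic |
| Analysis (section 4) | No summary, subgroup or covariate by route |

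**3. What a combined rate would represent.** Let s of the 30 egg children enter by the second route. Let p_h and p_s be the tolerance rates in the history-positive and sensitised-only children.

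- Combined rate = (1 − s/30) × p_h + (s/30) × p_s
- Combined rate − p_h = (s/30) × (p_s − p_h)

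None of s, p_h or p_s is in the documents, so neither the size nor the sign of the difference follows from them. With s = 6 (20% of 30, an assumption) the difference is 0.2 × (p_s − p_h): a gap of 20 points between routes moves the combined rate by 4 points, in whichever direction the gap runs.

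If one assumes that sensitised-only children do better (p_s from 0.80 to 1.00, p_h from 0.50 to 0.70, s from 3 to 15), the excess runs from (3/30) × (0.80 − 0.70) = 1 point to (15/30) × (1.00 − 0.50) = 25 points. That range reflects the assumptions and is not an estimate.

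If the denominator is 30, one child is 1/30 = 3.3 points. Even this is conditional, because it is not stated whether egg controls enter the baseline denominator.

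**4. Whether one tolerance rule can serve at both time points.** The baseline baked egg doses in section 3 are 0.11, 0.22, 0.44 and 1.1 g of protein.

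- Total: 0.11 + 0.22 + 0.44 + 1.1 = 1.87 g
- Largest single dose: 1.1 g
- Section 4 threshold: 2 g, so the total falls short by 2 − 1.87 = 0.13 g

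A child who completes the baseline challenge has therefore not received the amount in the section 4 rule. The 2 g figure does match the egg muffin given at the 6-month escalation. The documents do not say which criterion defines tolerance at baseline.

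**5. Precision of a split.** Exact (Clopper-Pearson) 95% intervals near one half, with assumed subset sizes:

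| Count | Interval |
|---|---|
| 15/30 | 31% to 69% |
| 12/24 | 29% to 71% |
| 3/6 | 12% to 88% |

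A test between routes would be weak. For assumed rates of 0.60 and 0.90 at two-sided 0.05, power is about 22%, 37% and 47% for s = 6, 10 and 15.

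For the ROC analysis, the Hanley-McNeil standard error at an AUC of 0.70 with 12 tolerant and 12 non-tolerant children (an assumed split) is 0.108. The interval is 0.70 ± 1.96 × 0.108, or about 0.49 to 0.91.

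**The case against.** The case against has substance, and several parts of it stand.

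- **Pooling is silence, not a statement.** No sentence in section 4 combines the two routes. The planned categorical comparisons of clinical variables could include reaction history, although it is not named. The accurate statement is that reporting by route is not specified.
- **No effect is shown.** A reader might infer that the egg tolerance rate is inflated. The documents do not support that. They give no rates, the sign depends on an unknown difference, and the history-positive children may themselves include some who are not clinically reactive.
- **The history-positive set is not confirmed either.** Its criterion asks only for a suggestive history with positive tests, and it too has no unbaked challenge at baseline. It is closer to the stated population but not proof of allergy. The sensitised-only route remains the clearest mismatch, since a reaction on eating egg cannot have been observed.
- **The biomarker analysis is not invalidated.** A reader might infer that it is. For the target in section 4, tolerance to baked products, a never-allergic child who tolerates is correctly classed. The difficulty arises only if a cut-off is read as predicting the acquisition of tolerance, as the secondary objective words it. A repeat in the subset would be too imprecise to carry weight.
- **Admitting these children may be deliberate.** Nothing here argues for excluding them.

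The absence of an unbaked baseline challenge also limits what can be said about tolerance acquired during the year in every child, milk included. That is a separate matter and does not follow from the entry route.

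What survives is the mismatch between the label and the entry criteria, with nothing later in the plan to resolve it.

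**Conclusion.** The point holds as one of labelling and reporting. The egg group as defined is wider than the allergic population named in the objective and the sample size, and following the plan as written yields an egg rate attributed to allergic children that may include children who were never allergic. The mismatch is certain from the text. Its numerical effect is unknown in size and direction, and every figure for it above rests on an assumed route mix and assumed rates. It should be corrected because correction costs almost nothing and lets the trial answer its own question about egg-allergic children. It does not show that the trial's result would be biased in a known direction. The 1.87 g total against the 2 g rule needs no assumption, and those passages must be reconciled before any baseline tolerance rate is reported, by route or overall.

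**What to change.** 1. Record the entry route (suggestive history, or sensitised without ingestion) for every egg child, including any egg controls, and state how the controls divide by food.
2. Report the baseline baked egg challenge result and the 12-month challenge result by route, as counts with exact 95% confidence intervals and no test between routes.
3. State the tolerance criterion and the denominator at each time point, and reconcile the baseline baked egg doses in section 3 with the 2 g rule in section 4.
4. Label the combined figure egg-sensitised or egg-allergic. Base statements about clinical egg allergy on the history-positive children, noting that they too are not challenge-confirmed.
5. A repeat of the egg ROC analysis in history-positive children is optional and exploratory only.

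**Cost:** the route is known at enrolment from the criterion met, so items 1, 2 and 4 need one recorded item and some SAP and reporting text, with no change to sample size or visits. Item 3 needs a decision by the investigators, since the two passages do not agree. The drawback is small subsets: a sensitised-only group of 6 with 3 tolerant would have an interval of 12% to 88%, so the split can describe but not compare.

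### Baked milk doses 1–3 are labelled as if a cookie held 0.30 g of milk protein, 9.1% above the stated 0.275 g on which doses 4–5 and the 6-month dose rest

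*Combined protocol and SAP*

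**What the plan says.** All references are to the combined protocol and SAP.

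- **Section 3, Initial baked milk challenge**, gives the protein content of the cookie: "each containing 0.275 g of milk protein".
- The same list labels the three part-cookie steps: "Dose 1: 0.0375 g protein (1/8 cookie"), "Dose 2: 0.075 g protein (1/4 cookie") and "Dose 3: 0.15 g protein (1/2 cookie").
- The two whole-cookie steps follow: "Dose 4: 0.275 g protein (1 full cookie") and "Dose 5: 0.55 g protein (2 cookies").
- **Section 3, 6-month dose escalation**, sets four of these "cookies = 1.1 g milk protein".
- **Section 2, secondary objectives**, includes: "To determine the individual reaction threshold dose that would allow patients to consume trace amounts of the allergen".
- **Section 4, Statistical analysis**, classes a milk participant as tolerant or not by a criterion of 1 g of cow's milk protein. It describes no analysis of reaction thresholds.

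No rounding rule and no second cookie content appear anywhere.

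**The concern.** The gram labels do not all follow from the stated cookie content. From dose 3 to dose 4 the amount of cookie doubles, but the labelled protein rises only from 0.15 to 0.275 g, a factor of 1.83. The first three labels therefore rest on a different content from the last two.

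The use at risk is the reaction threshold. Doses 1–3 are the lowest baked milk steps, where a threshold relevant to trace intake would be seen. If thresholds are taken from the printed grams and 0.275 g is the true content, a child who reacts at one of these steps is recorded as having a higher threshold than the real one. That is the less cautious direction for advice on traces.

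**Working it through.** **Inputs** (section 3): stated content 0.275 g per cookie; amounts of 1/8, 1/4, 1/2, 1 and 2 cookies, and 4 cookies at 6 months; the printed gram labels. The 1 g criterion is from section 4.

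**Step 1. Try to reproduce the labels.** Expected protein = cookies × 0.275 g. Implied content = label ÷ cookies.

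| Step | Cookies | Label (g) | Cookies × 0.275 (g) | Implied content (g per cookie) | Label excess |
|---|---|---|---|---|---|
| Dose 1 | 1/8 | 0.0375 | 0.034375 | 0.300 | 3.125 mg (9.1%) |
| Dose 2 | 1/4 | 0.075 | 0.06875 | 0.300 | 6.25 mg (9.1%) |
| Dose 3 | 1/2 | 0.15 | 0.1375 | 0.300 | 12.5 mg (9.1%) |
| Dose 4 | 1 | 0.275 | 0.275 | 0.275 | 0 |
| Dose 5 | 2 | 0.55 | 0.55 | 0.275 | 0 |
| 6 months | 4 | 1.1 | 1.1 | 0.275 | 0 |

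The last three labels reproduce exactly and the first three do not. The relative excess is 0.300/0.275 − 1 = 9.1%.

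**Step 2. Is it rounding of the final values?** No. To four decimals the products are 0.0344, 0.0688 and 0.1375, and rounding to two or three decimals does not give the three labels either. Taking 0.275 as 0.3 before dividing would give all three. So would taking 0.1375 as 0.15 and halving twice. The document does not say which happened, and the conclusion does not depend on it.

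**Step 3. Cumulative dose**, in case thresholds are reported that way:

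| Through dose | From labels (g) | At 0.275 g per cookie (g) | Ratio |
|---|---|---|---|
| 1 | 0.0375 | 0.034375 | 1.091 |
| 2 | 0.1125 | 0.103125 | 1.091 |
| 3 | 0.2625 | 0.240625 | 1.091 |
| 4 | 0.5375 | 0.515625 | 1.042 |
| 5 | 1.0875 | 1.065625 | 1.021 |

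The absolute excess is 21.875 mg from dose 3 onward.

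**Step 4. The opposite case.** If the true content is 0.30 g, doses 1–3 are correct. Dose 4 should then read 0.30 g, dose 5 should read 2 × 0.30 = 0.60 g, and the 6-month dose 4 × 0.30 = 1.2 g.

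**Step 5. Effect on the 1 g criterion.** The five doses add up to 0.125 + 0.25 + 0.5 + 1 + 2 = 3.875 cookies. That is 3.875 × 0.275 = 1.0656 g or 3.875 × 0.30 = 1.1625 g, both above 1 g. The largest single challenge dose (0.55 or 0.60 g) is below 1 g on either content, and the 6-month dose (1.1 or 1.2 g) is above it. Classification after a completed challenge therefore does not turn on which content is right, whether the criterion is read as a single or a cumulative dose.

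**Step 6. Comparison within the section.** The four baked egg doses are consistent: 0.11/0.5, 0.22/1, 0.44/2 and 1.1/5 all give 0.22 g per cookie.

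**The case against.** The strongest case against the point is that nothing planned depends on these labels. Section 4 contains no threshold analysis, the 1 g classification is unchanged, and each step is defined by a cookie fraction that staff can follow without the gram figure. Harm needs two conditions: thresholds are read from the labels, and 0.275 g is the true content. Even then, 9.1% is small beside dose steps that roughly double. All of this stands, and it is why the point is minor.

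A second argument is that the liquid milk table in the same section is also inexact and is let pass. At 3 g/100 mL, the 0.3, 3, 9, 30 and 90 mL rows hold 0.009, 0.09, 0.27, 0.9 and 2.7 g but are labelled 0.01, 0.1, 0.3, 1 and 3 g, which is 11.1% high. The difference is that this table is said to follow PRACTALL, so its figures can be read as nominal steps. The cookie list cites no nominal scheme, states its own content, and gives dose 1 to four decimals. The comparison supports calling this a labelling slip but does not remove it.

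A third argument is that the documents cannot show whether 0.275 or 0.30 g is true. That is correct and affects the direction of the error, not its existence. If 0.30 g is true, thresholds at doses 4 and 5, taken as single doses, would rise by 9.1% and those at doses 1–3 would stand.

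**Conclusion.** The point holds. The baked milk challenge uses two protein contents for one cookie, and some printed doses are wrong whichever is true. Taking the stated 0.275 g as correct, single doses 1–3 are overstated by 9.1%. Cumulative doses are overstated by 9.1% through dose 3, 4.2% through dose 4 and 2.1% through dose 5.

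The inconsistency itself is certain. Its direction rests on the stated content being the true one, and its effect on results rests on thresholds being read from the gram labels. There is no effect on what children are given. Severity: minor.

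**What to change.** 1. Check the protein content on the product label.
2. If it is 0.275 g, relabel doses 1–3 as 0.0344, 0.0688 and 0.1375 g. If it is 0.30 g, correct the stated content to 0.30 g, doses 4–5 to 0.30 and 0.60 g, and the 6-month dose to 1.2 g.
3. Add one line to section 4: a reported milk threshold is the number of cookies or mL actually taken times the stated protein content, identified as single or cumulative dose.

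As an optional clarification, not a correction, the gram column of the liquid milk table could be marked as nominal PRACTALL steps.

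The cost is one look at the product label, a few corrected figures and one sentence. No dose changes and no new data are needed. If 0.275 g is confirmed, any thresholds already taken from the labels become slightly lower: by 9.1% of the corrected value at doses 1–3, and by less at doses 4–5 if cumulative.
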